- In Case of Injury: This section is required for any research involving more than minimal risk, and for minimal risk research that presents the potential for physical harm (e.g., research involving blood draws).
 N/A
 - a. Will medical treatment be available if research-related injury occurs? Write here
 - b. Where and from whom may treatment be obtained? *Write here*
 - c. Are there any limits to the treatment being provided? Write here
 - d. Who will pay for this treatment? *Write here*
 - e. How will the medical treatment be accessed by subjects? Write here

IMPORTANT REMINDERS

Will this study have a billable service? Yes \Box No \boxtimes

A billable service is defined as any service rendered to a study subject that, if he/she was not on a study, would normally generate a bill from either Yale-New Haven Hospital or Yale Medical Group to the patient or the patient's insurer. The service may or may not be performed by the research staff on your study, but may be provided by professionals within either Yale-New Haven Hospital or Yale Medical Group (examples include x-rays, MRIs, CT scans, specimens sent to central labs, or specimens sent to pathology). Notes: 1. There is no distinction made whether the service is paid for by the subject or their insurance (Standard of Care) or by the study's funding mechanism (Research Sponsored). 2. This generally includes new services or orders placed in EPIC for research subjects.

If answered, "yes", this study will need to be set up in OnCore, Yale's clinical research management system, for Epic to appropriately route research related charges. Please contact [contact]

Are there any procedures involved in this protocol that will be performed at YNHH or one of its affiliated entities? Yes □ No ⊠

If Yes, please answer questions a through c and note instructions below.

a. Does your YNHH privilege delineation currently include the **specific procedure** that you will perform? **Yes No**

b. Will you be using any new equipment or equipment that you have not used in the past for this procedure? **Yes** □ **No** □

c. Will a novel approach using existing equipment be applied? Yes \Box No \Box

If you answered "no" to question 4a, or "yes" to question 4b or c, please contact the YNHH Department of Physician Services ([name]) for prior approval before commencing with your research protocol.

IMPORTANT REMINDER ABOUT RESEARCH AT YNHH

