The following pre-specified secondary outcomes will be measured to determine the effect of the various technologies on patient outcomes, quality of patient care, clinical efficiency, and both patient and provider satisfaction with the products.

	le l	Patient Outcomes			
	Outcome	Measure	Data Storage		
	Hospital Admissions	Epic, Ping	RedCap (Yale)		
		Rates of prescribing and dosing of beta			
	Guideline directed medical therapy	blockers, ACEi/ARBs, spironolactone (via	RedCap (Yale)		
• • • • • • • •		Surescripts)			
Adverse Events	ED visits	Hospital records	RedCap (Yale)		
	Mortality	Hospital records	RedCap (Yale)		
	Clinic no show rates	Medical records	RedCap (Yale)		
	AKI/AKD Development	Medical records	RedCap (Yale)		
	Satisfaction with device/technology	NPS score via post-study survey	HIPAA-compliant dashboard (Medullan)		
11 h 11	Frequency of use (overall and feature level)	Post-study survey	HIPAA-compliant dashboard (Medullan)		
Usability	Content rating	Post-study survey	HIPAA-compliant dashboard (Medullan)		
	Perceived impact	Post-study survey	HIPAA-compliant dashboard (Medullan)		
	· ·	linician Outcomes			
	Outcome	Measure	Data Storage		
	Amount of intravisit contact	Telephone logs in medical record			
	Number of clinic visits	Medical records			
Clinical Efficiency	Time devoted to patient care	Number of chart openings per patient	RedCap (Yale)		
	Provider assessment of global disease severity	Post-study survey			
Satisfaction	Effect on workload and efficiency	Post-study survey			
		tics of Digital Health Products			
	Outcome	Measure	Data Storage		
Completion of subject enrollment	Number of enrolled patients				
	Number of incomplete enrollments				
Completion rate of baseline assessments	Number of complete and incomplete aseessments				
400000000000000000000000000000000000000	Time to complete initial assessments				
Completion of digital health product set-up	Number of complete and incomplete product set-ups				
product set-up	Number of products that completed initial data sync				
Subject drop-off rates	Percent of patients with last screen assessed in session	Continuous data collection via product	HIDAA compliant dackhoard (Modullan)		
	Number of active (>1 login per week) patients per week	databases	HIPAA-compliant dashboard (Medullan)		
	Average number of logins per week				
	Number of patients without logins per week				
Device usage	Statistic for each session (time of day, day of week,				

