Eligibility will be assessed by on site and central study coordinators who will prospectively review our patient dashboard and further consult the electronic medical record for inclusion and exclusion criteria of patients currently enrolled in the clinics. Criteria will be further confirmed during the patient's in clinic visit or via a telephone call with a study coordinator prior to consent. Digital and technology literacy is not considered an eligibility requirement, as one main goal of the study is to assess whether these digital health products would be efficacious and applicable for this patient demographic. Once a patient has consented to participate in the study and has been enrolled, he/she will be asked to take a digital literacy survey as a means for baseline assessment and to track improvement of this metric over the course of the study.

- 10. **Risks:** Describe the reasonably foreseeable risks, including risks to subject privacy, discomforts, or inconveniences associated with subjects participating in the research. General study risks:
 - Loss of confidentiality: We will be collecting patient information and data, which is subject to loss of confidentiality in any clinical trial.
 - Physician burden: Physicians will be receiving additional information about their patients via the study devices, which may increase workload via additional time spent on patient care, reviewing medical record data, and/or ordering additional tests and reviewing subsequent results.
 - Overtreatment: It is possible that patients in the intervention group may be at risk for more aggressive therapies or treatments and increased medical costs as a consequence of closer monitoring.

Bodyport-specific risks and restrictions:

- The Bodyport scale cannot be exposed to extreme temperatures or submerged in liquid.
- The scale should not be used if the glass surface is cracked or chipped, as this could result in personal injury.
- The scale should not be used of the surface is wet, as this could cause a slippery surface that could result in personal injury.

- 11. Minimizing Risks: Describe the manner in which the above-mentioned risks will be minimized.

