- Risk of overtreatment: The technologies in this study are designed to relay additional information to providers that can be used *in conjunction* with all other medical information available to them to aid in the clinical decision-making process. Any additional tests or treatments should be prescribed using their own clinical judgement based on all available information sources regarding the patient's condition. We will appropriately educate providers about the nature of the study devices and the information that each provides so that physicians can understand how to best incorporate this information into their decision-making.
- Device-specific risks for Bodyport: We will discuss the above risks with the patient before and during the consent process to ensure the patient understand the risks and proper use of the device. The patient will be shown product manuals and informational materials for the scale and will be given the opportunity to answer any questions. Once enrolled into the study and assigned to a treatment group, patients will be given manuals and instructions for the device they receive, and will receive a thorough orientation to the product by a study coordinator who will emphasize any risks involved.
- 12. Data and Safety Monitoring Plan: Include an appropriate Data and Safety Monitoring Plan (DSMP) based on the investigator's risk assessment stated below. (Note: the HIC will make the final determination of the risk to subjects.)

- a. What is the investigator's assessment of the overall risk level for subjects participating in this study? This protocol presents minimal risk to all subjects.
- b. If children are involved, what is the investigator's assessment of the overall risk level for the children participating in this study? N/A
- c. Include an appropriate Data and Safety Monitoring Plan. Examples of DSMPs are available here http://your.yale.edu/policies-procedures/forms/420-fr-01-data-and-safety-monitoring-plans-templates for
 - i. Minimal risk
 - ii. Greater than minimal

Assessing the Efficacy of Digital Health Technology in the Management of Congestive Heart Failure: An Evaluation of Four Novel Digital Health Products

420 FR.1 PI: F. [name] MSCE

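### The protocol names personal injury from the BodyPort scale as a risk, yet answers N/A to an injury section that its own wording requires, and no scheduled contact is stated to ask about falls or injuries

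*Combined protocol and SAP*

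**What the plan says.** **The risk.** Section I, item 10 (Risks) has a block specific to BodyPort. On damaged glass it reads: "The scale should not be used if the glass surface is cracked or chipped, as this could result in personal injury". On a wet surface it warns against use, "as this could cause a slippery surface that could result in personal injury".

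**The injury section.** Section VI, In Case of Injury, states when it must be filled in: "This section is required for any research involving more than minimal risk, and for minimal risk research that presents the potential for physical harm". The answer given is N/A, and the items beneath keep their template prompts, for example "Will medical treatment be available if research-related injury occurs? Write here".

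**Prevention.** Section I, item 11 (Minimizing Risks) handles the BodyPort risks through information: "We will discuss the above risks with the patient before and during the consent process". It adds manuals and a coordinator-led orientation to the device. Item 8 excludes patients who cannot stand unaided for thirty seconds and those above 400 pounds.

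**Detection.** Item 12 (Data and Safety Monitoring Plan) rates the study minimal risk and says adverse events are not expected. It gives the principal investigator bi-monthly safety reviews and has all adverse events passed to the research monitors within 5 days of the principal investigator learning of them. The outcomes table in item 4 lists admissions, ED visits, mortality, clinic no-shows and "AKI/AKD Development", but no fall or injury.

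**The concern.** The protocol answers one factual question in two ways. Item 10 treats physical injury from the scale as reasonably foreseeable. The N/A in Section VI implies that the study has no potential for physical harm. As a result, that section does not say whether treatment would be available after an injury, where, within what limits, or who would pay.

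The second issue is how the trial would learn of an injury. BodyPort is not FDA-cleared and is used under the investigators' own assessment of non-significant risk (Section II, Devices). Injury from the scale is the only direct physical injury that the protocol attributes to an intervention. If nobody is routinely asked, the end-of-trial count reflects what patients chose to mention or what reached a chart, and a count of zero would be hard to interpret.

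**Working it through.** The plan states no figure on this point to reproduce, so the check is mainly a comparison of text, followed by a short calculation of what a zero count would mean.

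**Step 1: does the injury section apply?** Its condition has two limbs: more than minimal risk, or minimal risk with potential for physical harm. Item 12 places the study at minimal risk, so the first limb is not met. Item 10 says twice that personal injury could result, so the second limb is met on the protocol's own words. The template instructions reserve a Not Applicable answer for sections that do not apply. N/A is therefore inconsistent with item 10.

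**Step 2: does any scheduled contact ask about injury?**
- Days 1-89: clinic visits every 2-3 weeks, with an opportunity to meet a coordinator. The listed instruments are usability and satisfaction surveys (intervention arms), the KCCQ, literacy questionnaires and medication adherence. Injury is not mentioned.
- Day 90 and day 180: the same kinds of instrument. The usability survey covers ease of use, frequency, satisfaction and perceived impact. Injury is not mentioned.
- Days 90-179: monthly calls to follow progress, check product use and take questions. Injury is not mentioned.

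**Step 3: what routes remain?** A patient may volunteer the event at a visit or call. Staff on the technical hotline escalate problems that turn out to be medical (item 11). Provider notes are collected (Section IV, item 1), and ED visits come from hospital records, with no stated attribution to the device. All of these are passive.

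**Step 4: how do the reporting rules treat a minor scale injury?** The Reportable Events definition in item 12 needs an event that is serious or life-threatening, is unanticipated or more frequent than expected, and is at least possibly related. A non-serious injury of the named kind falls outside it. The later sentence on all adverse events would include it, but only once the principal investigator knows of it. Judging whether a named event occurs more often than expected needs an expected frequency and a systematic count. The protocol gives neither.

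**Step 5: what would zero mean?** Inputs: 50 patients per arm (item 13) and 180 days of follow-up.
- Exposure: 50 × 180 = 9,000 uses at most. This is a ceiling, because use is voluntary and the device is mailed after enrollment.
- Every patient asked, zero injured: solving (1 − p)^50 = 0.05 gives p = 1 − 0.05^(1/50) = 5.8%. The rule of three gives 3/50 = 6%.
- If only 40 answered (the per-arm number before inflation, used here as an assumption): 3/40 = 7.5%.
- Passive capture: suppose a share s of injured patients comes to light. Zero reports then bounds the injury risk at about 6%/s. The documents give no value for s. As illustrative assumptions, s = 0.5 gives 12% and s = 0.25 gives 24%.

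**The case against.** The case on the other side has real weight.

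- **The risk is monitored.** A reader might infer that scale injuries go unmonitored, that one treated at home leaves no record, or that such injuries cannot be counted. The documents do not support this. Item 12 has regular safety review and reporting of every known adverse event. Patients are seen every 2-3 weeks and then called monthly, hotline staff escalate medical problems, and provider notes are collected. Any of these could bring an injury to light without an ED visit. What stands is that none is stated to ask.
- **The risk is provided for in part.** The eligibility limits, manuals and orientation are genuine prevention, but they do not detect an injury. On treatment and payment, the consent form was not in the text available for this review and may contain injury terms. Only the N/A itself can be criticised.
- **The outcomes table is not a safety form.** It lists pre-specified secondary outcomes, and its row grouping is unclear in the extracted text. The absence of falls from it does not show their absence from adverse event reporting. It does show that no count by arm is planned there.
- **Standing on a scale is an everyday act.** That may explain the N/A. But the section's condition is potential for physical harm, not its degree, and item 10 asserts that potential.
- **The unfilled prompts are not a second defect.** They follow from the N/A.
- **A trial of this size cannot prove minimal risk.** This is correct. Minimal-risk and non-significant-risk status are prospective assessments, and a 6% bound would not settle either.

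**Conclusion.** The inconsistency between Section I, item 10 and Section VI is established on the face of the protocol, and the two must be reconciled. It is also established that no listed outcome and no described contact asks about falls or device injuries, so capture is passive.

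The conclusion goes no further. To read the plan as leaving the risk unmonitored, or wholly unprovided for, would ignore item 12 and the prevention measures in items 8 and 11.

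The consequence is limited: zero reports could not be read as zero injuries. With solicited capture in about 50 patients, zero would carry an upper 95% bound of about 6%, which describes the risk and does not show it to be minimal. With passive capture, the bound on true injuries is wider by an unknown factor. These figures assume about 50 BodyPort patients in follow-up and, for the 6%, that all of them are asked and answer accurately. Nothing here touches the primary outcome, alpha, sample size or primary analysis. The change is worth making for patient safety and because the form's own rule calls for it.

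**What to change.** 1. Replace the N/A in Section VI with answers to items a to e, so that the section agrees with Section I, item 10 and with the consent form. The content of those answers is for the investigators and the IRB.
2. Add one standard question on any fall or injury since the last contact, including while using the study product. Ask it in all four arms, so that a background level is available and ascertainment does not differ by arm. Use contacts that already exist: coordinator meetings at clinic visits in days 1-89, the day-90 session, the monthly calls and the day-180 close-out. Starting before day 90 avoids a three-month recall period. Record the answer in one REDCap field.
3. Tabulate the answers by arm, descriptively, at the existing bi-monthly safety reviews.

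The cost is a protocol amendment, one field and slightly longer contacts, with no extra visits or staff. Recording device injuries only through the existing adverse event route would be a smaller change, but without the question it would leave capture passive.
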